2.3.2. Benefit Assessment

Benefits to individual participants enrolled in the study may be:

- Receipt of a further dose of an efficacious or potentially efficacious COVID-19 vaccine that may convey better protection against the SARS-CoV-2 wild-type (ancestral) strain and/or variants [original protocol and amendments 1 and 2: during a global pandemic].
- Contributing to research to help others [original protocol and amendments 1 and 2: in a time of global pandemic].

2.3.3. Overall Benefit/Risk Conclusion

Taking into account the measures to minimize risk to study participants as stated in Section 2.3.1, the potential risks identified in association with BNT162b RNA-based COVID-19 vaccines are justified by the anticipated benefits that may be afforded to healthy participants.

3. OBJECTIVES, ENDPOINTS, AND ESTIMANDS

Refer to Table 1, Table 3, and Table 4 for details of the Cohort 2 group, Cohort 3 group, and Cohort 4 group, respectively.

Objectives	Estimands	Endpoints					
Primary Safety							
Cohort 1: To describe the safety and tolerability profile of BNT162b5 Bivalent (WT/OMI BA.2) 30 µg and BNT162b2 Bivalent (WT/OMI BA.1) 30 µg given as a second booster dose to COVID-19 vaccine—experienced participants 18 through 55 years of age.	 In participants receiving 1 dose of study intervention, the percentage of participants reporting: Local reactions for up to 7 days following the study vaccination Systemic events for up to 7 days following the study vaccination AEs from the study vaccination through 1 month after the study vaccination SAEs from the study vaccination through 6 months after the study vaccination 	 Local reactions (pain at the injection site, redness, and swelling) Systemic events (fever, fatigue, headache, chills, vomiting, diarrhea, new or worsened muscle pain, and new or worsened joint pain) AEs SAEs 					

Objectives	Estimands	Endpoints
Cohort 2: To describe the safety and tolerability profile of BNT162b2 Bivalent (WT/OMI BA.4/BA.5) 30 µg given as a second booster dose to BNT162b2-experienced participants 12 through 17, 18 through 55, and >55 years of age, and BNT162b2 Bivalent (WT/OMI BA.4/BA.5) 60 µg given as a second booster dose to BNT162b2-experienced participants 18 through 55 and >55 years of age.	 In participants receiving 1 dose of study intervention, the percentage of participants reporting: Local reactions for up to 7 days following the study vaccination Systemic events for up to 7 days following the study vaccination AEs from the study vaccination through 1 month after the study vaccination SAEs from the study vaccination through 6 months after the study vaccination 	 Local reactions (pain at the injection site, redness, and swelling) Systemic events (fever, fatigue, headache, chills, vomiting, diarrhea, new or worsened muscle pain, and new or worsened joint pain) AEs SAEs
Cohort 2 + Cohort 3 combined: To describe the safety and tolerability profile of BNT162b2 Bivalent (WT/OMI BA.4/BA.5) 30 µg given as a second booster dose to BNT162b2-experienced participants 18 through 55 and >55 years of age.	 In participants receiving 1 dose of study intervention, the percentage of participants reporting: Local reactions for up to 7 days following the study vaccination Systemic events for up to 7 days following the study vaccination AEs from the study vaccination through 1 month after the study vaccination SAEs from the study vaccination through 6 months after the study vaccination 	Local reactions (pain at the injection site, redness, and swelling) Systemic events (fever, fatigue, headache, chills, vomiting, diarrhea, new or worsened muscle pain, and new or worsened joint pain) AEs SAEs
Cohort 4a: To describe the safety and tolerability profile of BNT162b2 Bivalent 30 µg, BNT162b5 Bivalent 30 µg, BNT162b6 Bivalent 30 µg, BNT162b7 Bivalent 30 µg, and BNT162b7 Monovalent 30 µg given to mRNA COVID-19 vaccine–experienced participants 18 through 55 years of age.	 In participants receiving 1 dose of study intervention, the percentage of participants reporting: Local reactions for up to 7 days following the study vaccination Systemic events for up to 7 days following the study vaccination AEs from the study vaccination through 1 month after the study vaccination SAEs from the study vaccination through 6 months after the study vaccination 	 Local reactions (pain at the injection site, redness, and swelling) Systemic events (fever, fatigue, headache, chills, vomiting, diarrhea, new or worsened muscle pain, and new or worsened joint pain) AEs SAEs

Objectives	Estimands	Endpoints
	Primary Immunogenicity	
Cohort 1: To describe the immune response to BNT162b5 Bivalent (WT/OMI BA.2) 30 µg and BNT162b2 Bivalent (WT/OMI BA.1) 30 µg given as a second booster dose to COVID-19 vaccine–experienced participants 18 through 55 years of age.	 In participants complying with the key protocol criteria (evaluable participants): GMT at baseline and 1 month after the study vaccination for each strain-specific neutralizing titer GMFR from before the study vaccination to 1 month after the study vaccination for each strain-specific neutralizing titer Percentages of participants with seroresponse^b at 1 month after the study vaccination for each strain-specific neutralizing titer 	SARS-CoV-2 Omicron (BA.2)— neutralizing titers SARS-CoV-2 Omicron (BA.1)— neutralizing titers SARS-CoV-2 reference-strain ^c — neutralizing titers
Cohort 2/Group 4 + Cohort 3/ Group 2 combined: To demonstrate the superiority with respect to level of neutralizing titer and noninferiority with respect to seroresponse rate of the anti-Omicron BA.4/BA.5 immune response after BNT162b2 Bivalent (WT/OMI BA.4/BA.5) 30 µg compared to after BNT162b2 30 µg ^d given as a second booster dose to BNT162b2-experienced participants >55 years of age.	 In participants complying with the key protocol criteria (evaluable participants): GMR of the Omicron (BA.4/BA.5)—neutralizing titers 1 month after BNT162b2 Bivalent (WT/OMI BA.4/BA.5) to 1 month after BNT162b2, given as a second booster dose in BNT162b2-experienced participants The difference in percentages of participants with seroresponse to the Omicron BA.4/BA.5 strain at 1 month after BNT162b2 Bivalent (WT/OMI BA.4/BA.5) and at 1 month after BNT162b2 given as a second booster dose in BNT162b2-experienced participants 	• SARS-CoV-2 Omicron (BA.4/BA.5)— neutralizing titers

Objectives	Estimands	Endpoints
Cohort 2/Group 2 + Cohort 3/Group 1 combined and Cohort 2/Group 4 + Cohort 3/Group 2 combined: To demonstrate the noninferiority with respect to level of neutralizing titer and with respect to seroresponse rate of the anti-Omicron BA.4/BA.5 immune response after BNT162b2 Bivalent (WT/OMI BA.4/BA.5) 30 µg given as a second booster dose to BNT162b2-experienced participants 18 through 55 years of age compared to participants >55 years of age.	In participants complying with the key protocol criteria (evaluable participants): • GMR of the Omicron (BA.4/BA.5)— neutralizing titers at 1 month after BNT162b2 Bivalent (WT/OMI BA.4/BA.5) given as a second booster dose in BNT162b2-experienced participants 18 through 55 years of age compared to participants >55 years of age • The difference in percentages of participants with seroresponse to the Omicron BA.4/BA.5 strain at 1 month after BNT162b2 Bivalent (WT/OMI BA.4/BA.5) given as a second booster dose in BNT162b2-experienced participants 18 through 55 years of age compared to participants >55 years of age	• SARS-CoV-2 Omicron (BA.4/BA.5)— neutralizing titers
Cohort 2: To describe the immune response to BNT162b2 Bivalent (WT/OMI BA.4/BA.5) 30 µg or 60 µg and BNT162b2 Bivalent (WT/OMI BA.1) 30 µge or 60 µge given as a second booster dose to BNT162b2-experienced participants 12 through 17, 18 through 55,e and >55e years of age.	 In participants complying with the key protocol criteria (evaluable participants): GMT at baseline and 1 month after the study vaccination for each strain-specific neutralizing titer GMFR from before the study vaccination to 1 month after the study vaccination for each strain-specific neutralizing titer Percentages of participants with seroresponse^b at 1 month after study vaccination for each strain-specific neutralizing titer 	SARS-CoV-2 Omicron (BA.4/BA.5)— neutralizing titers SARS-CoV-2 Omicron (BA.1)— neutralizing titers SARS-CoV-2 reference-strain ^c — neutralizing titers
Cohort 4 ^a : To describe the immune response to BNT162b2 Bivalent 30 µg, BNT162b5 Bivalent 30 µg, BNT162b6 Bivalent 30 µg, BNT162b7 Bivalent 30 µg, and BNT162b7 Monovalent 30 µg given to mRNA COVID-19 vaccine–experienced participants 18 through 55 years of age.	In participants complying with the key protocol criteria (evaluable participants): • GMT at baseline and 1 month after the study vaccination for each strain-specific neutralizing titer • GMFR from before the study vaccination to 1 month after the study vaccination for each strain-specific neutralizing titer • Percentages of participants with seroresponse ^b at 1 month after the study vaccination for each strain-specific neutralizing titer	SARS-CoV-2 Omicron (BA.4/BA.5)— neutralizing titers SARS-CoV-2 reference-strain ^c — neutralizing titers

Objectives	Estimands	Endpoints
	Secondary Immunogenicity	
Cohort 2/Group 4 + Cohort 3/Group 2 combined: To demonstrate the noninferiority of the anti–reference-strain immune response after BNT162b2 Bivalent (WT/OMI BA.4/BA.5) 30 µg compared to BNT162b2 30 µg ^d given as a second booster dose in BNT162b2-experienced participants >55 years of age.	In participants complying with the key protocol criteria (evaluable participants): • GMR of the reference-strain—neutralizing titers at 1 month after BNT162b2 Bivalent (WT/OMI BA.4/BA.5) and at 1 month after BNT162b2 given as a second booster dose in BNT162b2-experienced participants	• SARS-CoV-2 reference-strain ^c — neutralizing titers
Cohort 2/Group 2 + Cohort 3/Group 1 combined ^f and Cohort 2/Group 4 + Cohort 3/Group 2 combined: To describe the immune response to BNT162b2 Bivalent (WT/OMI BA.4/BA.5) 30 µg compared to BNT162b2 30 µg ^d given as a second booster dose to BNT162b2-experienced participants 18 through 55 and >55 years of age.	 In participants complying with the key protocol criteria (evaluable participants): GMT at baseline and 1 month after the study vaccination for each strain-specific neutralizing titer GMFR from before the study vaccination to 1 month after the study vaccination for each strain-specific neutralizing titer Percentages of participants with seroresponse^b at 1 month after the study vaccination for each strain-specific neutralizing titer 	 SARS-CoV-2 Omicron (BA.4/BA.5)— neutralizing titers SARS-CoV-2 reference-strain^c— neutralizing titers
	Exploratory	
Cohort 1: To describe the immune response to BNT162b5 Bivalent (WT/OMI BA.2) 30 µg and BNT162b2 Bivalent (WT/OMI BA.1) 30 µg given as a second booster dose to COVID-19 vaccine–experienced participants 18 through 55 years of age.	 In participants complying with the key protocol criteria (evaluable participants): At baseline and 7 days, 1 month, 3 months, and 6 months after study vaccination, GMT at each time point for each strain-specific neutralizing titer GMFR from before the study vaccination to 7 days after the study vaccination for each strain-specific neutralizing titer Percentages of participants with seroresponse^b at 7 days after the study vaccination for each strain-specific neutralizing titer 	 SARS-CoV-2 Omicron (BA.2)— neutralizing titers SARS-CoV-2 Omicron (BA.1)— neutralizing titers SARS-CoV-2 reference-strain^c — neutralizing titers

Objectives	Estimands	Endpoints
Cohort 2/Group 1, Cohort 2/Group 2 + Cohort 3/Group 1 combined, f Cohort 2/Group 4 + Cohort 3/Group 2 combined, f Cohort 2/Group 3, and Cohort 2/Group 5: To describe the immune response to BNT162b2 Bivalent (WT/OMI BA.4/BA.5) 30 µg or 60 µg compared to BNT162b2 30 µg f given as a second booster dose to BNT162b2-experienced participants 12 through 17, 18 through 55, and >55 years of age.	In participants complying with the key protocol criteria (evaluable participants): At baseline and 1 month, 3 months, and 6 months after study vaccination, GMT at each time point for each strain-specific neutralizing titer GMFR from before the study vaccination to each subsequent time point for each strain-specific neutralizing titer Percentages of participants with seroresponse ^b at each time point following vaccination for each strain-specific neutralizing titer	SARS-CoV-2 Omicron (BA.4/BA.5)— neutralizing titers SARS-CoV-2 reference-strain ^c — neutralizing titers
Cohort 4 ^a : To describe the immune response to BNT162b2 Bivalent 30 µg, BNT162b5 Bivalent 30 µg, BNT162b6 Bivalent 30 µg, and BNT162b7 Monovalent 30 µg given to mRNA COVID-19 vaccine—experienced participants 18 through 55 years of age.	 In participants complying with the key protocol criteria (evaluable participants): At baseline and 7 days, 1 month, 3 months, and 6 months after study vaccination, GMT at each time point for each strain-specific neutralizing titer GMFR from before the study vaccination to each time point after the study vaccination for each strain-specific neutralizing titer Percentages of participants with seroresponse^b at each time point after the study vaccination for each strain-specific neutralizing titer 	SARS-CoV-2 Omicron (BA.4/BA.5)— neutralizing titers SARS-CoV-2 reference-strain ^c — neutralizing titers
Cohort 1, Cohort 2 + Cohort 3 combined, and Cohort 4: To describe confirmed COVID-19 and severe COVID-19 cases in each vaccine and age group.		 Confirmed COVID-19 cases Confirmed severe COVID-19 cases Strain sequencing of COVID-19 cases
Cohort 1, Cohort 2 + Cohort 3 combined, and Cohort 4: To describe the immune response to SARS-CoV-2 infection at the time of the COVID-19 illness visit ^g and at the convalescent visit.		SARS-CoV-2— neutralizing titers previously specified for the respective cohorts
Cohort 1, Cohort 2 + Cohort 3 combined, and Cohort 4: To describe the immune response to other emerging variants (under monitoring, of interest, and/or of concern).		SARS-CoV-2— neutralizing titers for other variants (under monitoring, of interest, and/or of concern) not already specified

Objectives	Estimands	Endpoints
Cohort 2: To describe the cell-mediated immune response, and additional humoral immune response parameters, to the		-
reference strain ^c and Omicron in a subset of participants with PBMC samples collected.		

- a. The Cohort 4 bivalent vaccines target the SARS-CoV-2 Original strain and the Omicron variant (BA.4/BA.5 sublineage). The Cohort 4 monovalent vaccine targets the Omicron variant (BA.4/BA.5 sublineage).
- b. Seroresponse is defined as achieving a ≥4-fold rise from the baseline (before the study vaccination). If the baseline measurement is below the LLOQ, the postvaccination measure of ≥4 × LLOQ is considered seroresponse.
- Reference strain is also referred to as the Original, Wild Type, or ancestral strain (Wuhan-Hu-1; USA-WA1/2020).
- d. The participants >55 years of age from C4591031 Substudy E expanded cohort who received BNT162b2 30 μg as a second booster dose will be used as comparator group for this objective.
- e. A subset of approximately 100 participants in each age group (18 through 55 years of age, >55 years of age) and dose group (30 μg, 60 μg) from C4591031 Substudy E expanded cohort who received BNT162b2 Bivalent (WT/OMI BA.1) 30 μg or 60 μg as a second booster dose will be selected for this objective. The subset selected from C4591031 Substudy E will include similar percentage of participants with baseline positive SARS-CoV-2 infection status as the groups in Cohort 2 of this study whenever feasible.
- f. A subset of approximately 100 participants in each age group (18 through 55 years of age, >55 years of age) from C4591044 Cohort 2/Group 2 + Cohort 3/Group 1 combined and Cohort 2/Group 4 + Cohort 3/Group 2 combined who received BNT162b2 Bivalent (WT/OMI BA.4/BA.5) 30 μg and from the C4591031 Substudy E expanded cohort who received BNT162b2 30 μg as a second booster dose will be selected for this objective. The subset selected will include a similar percentage of participants with baseline positive SARS-CoV-2 infection status whenever feasible.
- g. If the COVID-19 illness visit is conducted as an in-person visit, a blood sample will be taken for this assessment. No blood samples will be obtained for remote (telehealth) COVID-19 illness visits.

4. STUDY DESIGN

4.1. Overall Design

This study is a randomized, active-controlled study to evaluate the safety, tolerability, and immunogenicity of new bivalent and monovalent vaccines. The study duration for each participant will be approximately 6 months. The study vaccine candidates are divided into cohorts, which may be studied in a staggered or parallel manner, as required by the clinical plan.

Refer to the schema in Section 1.2.

Based on review of safety or immunogenicity data of any study intervention group, at Pfizer's discretion, subsequent collection of blood samples from participants in that group may be halted and/or not analyzed and study visits or other procedures may be discontinued.

An EDMC will review cumulative unblinded data throughout the study. Refer to Appendix 1, Section 10.1.5.1.

Cohort 1 Design

For the purposes of this protocol, study intervention within this cohort refers to:

- BNT162b5 Bivalent (WT/OMI BA.2) 30 μg
- BNT162b2 Bivalent (WT/OMI BA.1) 30 μg

Participants 18 through 55 years of age will be randomized at a ratio of 1:1 to receive a single 30-µg dose of 1 of the 2 study interventions as a second booster dose. Participants will be stratified by the number of months since the last dose of COVID-19 vaccine received prior to randomization (3 to 6 months [90 to 180 days] or >6 months [>180 days]). Approximately 200 participants will be enrolled in this cohort.

Cohort 2 Design

For the purposes of this protocol, study intervention within this cohort refers to:

- BNT162b2 Bivalent (WT/OMI BA.4/BA.5) 30 μg
- BNT162b2 Bivalent (WT/OMI BA.4/BA.5) 60 μg

Participants 12 through 17 years of age who have received 3 prior doses of BNT162b2 (30-μg doses), with the most recent dose being 150 to 365 days prior to Visit 1 (Day 1), will receive a single 30-μg dose of BNT162b2 Bivalent (WT/OMI BA.4/BA.5) as a second booster dose (open-label). Participants 18 through 55 and >55 years of age who have received 3 prior doses of BNT162b2 (30-μg doses), with the most recent dose being 150 to 365 days prior to Visit 1 (Day 1), will be randomized 1:1 within each age group to receive BNT162b2 Bivalent (WT/OMI BA.4/BA.5) at either 30 μg or 60 μg as a second booster dose (observer-blind). Approximately 500 participants will be enrolled into this cohort per Table 1.

Table 1. Cohort 2 Design

	Cohort 2: BNT162b2 Bivalent (WT/OMI BA.4/BA.5)					
Group	Participant Age Group	Prior Doses of BNT162b2	Time Since Last Dose	Study Dose	Number of Participants	Randomization / Blind
1	12-17 years	3	150-365 days	30 μg	100	Open-label
2	18-55 years	3	150-365 days	30 μg	100	Randomized 1:1
3	18-55 years	3	150-365 days	60 μg	100	Observer-blind
4	>55 years	3	150-365 days	30 μg	100	Randomized 1:1
5	>55 years	3	150-365 days	60 μg	100	Observer-blind

To evaluate the immunogenicity objective for Cohort 2, a subset of approximately 100 participants in each age group (18 through 55 years of age, >55 years of age) and dose group (30 μ g, 60 μ g) from the C4591031 Substudy E expanded cohort who received Bivalent BNT162b2 (WT/OMI BA.1) 30 μ g or 60 μ g as a second booster dose will be selected as the control group for the descriptive immunogenicity summary (Table 2). The subset selected from C4591031 Substudy E will include similar percentage of participants with baseline positive SARS-CoV-2 infection status as the groups in Cohort 2 of this study whenever feasible.

Table 2. Cohort 2 Immunogenicity Control Groups From C4591031 Substudy E

	C4591031 Substudy E Subset				
Participant Age Group	Vaccine Group	Dose	Number of Participants		
18-55 years	Bivalent BNT162b2 (WT/OMI BA.1)	30 μg	100		
18-55 years	Bivalent BNT162b2 (WT/OMI BA.1)	60 µg	100		
>55 years	Bivalent BNT162b2 (WT/OMI BA.1)	30 μg	100		
>55 years	Bivalent BNT162b2 (WT/OMI BA.1)	60 μg	100		

Note: Vaccine group name in C4591031 Substudy E is "Bivalent BNT162b2 and BNT162b2 OMI."

Cohort 3 Design

For the purposes of this protocol, study intervention within this cohort refers to:

• BNT162b2 Bivalent (WT/OMI BA.4/BA.5) 30 μg

Participants 18 years of age and older who have received 3 prior 30-µg doses of BNT162b2, with the most recent dose being 150 to 365 days prior to Visit 1 (Day 1), will receive a single 30-µg dose of BNT162b2 Bivalent (WT/OMI BA.4/BA.5) as a second booster dose (open-label). Approximately 400 participants will be enrolled into this cohort per Table 3.

Table 3. Cohort 3 Design

	Cohort 3: BNT162b2 Bivalent (WT/OMI BA.4/BA.5)					
Group						Randomization / Blind
1	18-55 years	3	150-365 days	30 μg	200	Open-label
2	>55 years	3	150-365 days	30 μg	200	Open-label

Note: For certain safety and immunogenicity objectives, the 18- through 55-year age group and the >55-year age group will comprise participants from Cohorts 2 and 3 combined.

Combining Cohort 2 and Cohort 3, there will be approximately 300 participants in each age group who received BNT162b2 Bivalent (WT/OMI BA.4/BA.5) 30 µg. To evaluate the primary immunogenicity hypothesis for the >55-year age group of Cohort 2 and Cohort 3 combined, the participants >55 years of age from the C4591031 Substudy E expanded cohort who received BNT162b2 30 µg as a second booster dose will be used as comparator group (approximately 300 participants [Expanded Enrollment – Group 1]).

Cohort 4: Participants 18 through 55 years of age who have received 3 or 4 prior doses of a US-authorized mRNA COVID-19 vaccine, with the most recent dose being a bivalent vaccine at least 150 days prior to Visit 1 (Day 1), will be enrolled. The Cohort 4 bivalent vaccines target the SARS-CoV-2 Original strain and the Omicron variant (BA.4/BA.5 sublineage). The Cohort 4 monovalent vaccine targets the Omicron variant (BA.4/BA.5 sublineage). Participants will be randomized at a ratio of 1:1:1:1:1 to receive a single 30-μg dose of either BNT162b2 Bivalent, BNT162b5 Bivalent, BNT162b6 Bivalent, BNT162b7 Bivalent, or BNT162b7 Monovalent (observer-blind). Participants will be stratified by the number of prior doses (3 or 4 prior doses) of a US-authorized mRNA COVID-19 vaccine received prior to randomization.

Table 4. Cohort 4 Design

	Cohort 4: BNT162b Omicron BA.4/BA.5 Vaccine Candidates All Participants 18 Through 55 Years of Age					
Group	Study Intervention	Study Dose	Prior Doses of mRNA COVID-19 Vaccine	Time Since Last Dose	Number of Participants	Randomization / Blind
1	BNT162b2 Bivalent (Original/OMI BA.4/BA.5)	30 μg	3 or 4	≥150 days	60	Randomized 1:1:1:1:1
2	BNT162b5 Bivalent (Original/OMI BA.4/BA.5)	30 μg	3 or 4	≥150 days	60	Observer-blind
3	BNT162b6 Bivalent (Original/OMI BA.4/BA.5)	30 μg	3 or 4	≥150 days	60	
4	BNT162b7 Bivalent (Original/OMI BA.4/BA.5)	30 μg	3 or 4	≥150 days	60	
5	BNT162b7 Monovalent (OMI BA.4/BA.5)	30 μg	3 or 4	≥150 days	60	

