1.3. Schedule of Activities

The SoA table provides an overview of the protocol visits and procedures. Refer to the STUDY ASSESSMENTS AND PROCEDURES section of the protocol for detailed information on each procedure and assessment required for compliance with the protocol.

An unplanned potential COVID-19/MIS-C illness visit and unplanned potential COVID-19/MIS-C convalescent visit are required at any time between Visit 1 (vaccination) and Visit 5 (6-month follow-up visit) that COVID-19 symptoms are reported. During the 7 days following each dose, potential COVID-19/MIS-C symptoms that overlap with specific systemic events (ie, fever, chills, new or increased muscle pain, diarrhea, vomiting) should not trigger a potential COVID-19/MIS-C illness visit unless, in the investigator's opinion, the clinical picture is more indicative of a possible COVID-19/MIS-C illness rather than vaccine reactogenicity. For details, see Section 8.10.7.

The investigator may schedule visits (unplanned visits) in addition to those listed in the SoA table, in order to conduct evaluations or assessments required to protect the well-being of the participant. Based on review of safety or immunogenicity data of any study intervention group, at Pfizer's discretion, study visits, blood sample collection/analysis, or other procedures may be halted or discontinued.

								Notes
Visit Identifier	1	2	3	4	5	Unplanned	Unplanned	
Visit Description	Vax 1 Visit	1-Week Follow-Up Visit (Vax 1)	1-Month Follow-Up Visit (Vax 1)	3-Month Follow-Up Visit (Vax 1)	6-Month Follow-Up Visit (Vax 1)	Potential COVID-19 Illness Visit	Potential COVID-19 Convalescent Visit	The COVID-19 illness visit may be conducted as an in-person or telehealth visit. The COVID-19 illness visit is only conducted for symptomatic participants. See Section 8.10.7.
Visit Window	Day 1	6 to 8 Days After Visit 1	28 to 35 Days After Visit 1	84 to 98 Days After Visit 1	175 to 189 Days After Visit 1	Optimally Within 3 Days After Potential COVID-19 Illness Onset	28 to 35 Days After Potential COVID-19 Illness Visit	
Obtain informed consent and assent (if appropriate)	X							If vaccination is temporarily delayed, per Section 5.5, consent need not be obtained again on the day of vaccination.

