6.4.3. Blinding of the Sponsor

Cohort 1, Cohort 2, and Cohort 4: To facilitate rapid review of data in real time, the majority of Pfizer/BioNTech staff will be unblinded to study intervention allocation.

Cohort 3: Given the single study intervention arm, both groups are unblinded to the majority of Pfizer staff involved in the conduct of the study.

All Cohorts: All laboratory testing personnel will remain blinded to study intervention assigned/received throughout the study.

As this is a sponsor open-label study, the sponsor may conduct unblinded reviews of the data during the course of the study for the purpose of safety assessment and/or supporting clinical development.

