9.4. Interim Analyses

As C4591044 is a sponsor open-label, Phase 1/2/3 study, Pfizer may conduct unblinded reviews of the data during the course of the study for the purpose of safety assessment and/or supporting clinical development.

No formal interim analysis will be conducted. Statistical analyses will be carried out when the final data for specified objectives are available while the study is ongoing. The timing of these planned analysis and reporting events is described in Section 9.4.1.

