2.3. Study Design

This study is a randomized, active-controlled study to evaluate the safety, tolerability, and immunogenicity of new bivalent and monovalent vaccines. The study duration for each participant will be approximately 6 months. The study vaccine candidates are divided into cohorts, which may be studied in a staggered or parallel manner, as required by the clinical plan. Refer to the Schema in Figure 1.

Based on review of safety or immunogenicity data of any study intervention group, at Pfizer's discretion, subsequent collection of blood samples from participants in that group may be halted and/or not analyzed, and study visits or other procedures may be discontinued.

An EDMC will review cumulative unblinded data throughout the study.

Figure 1. Schema

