6.1.1.4. Serious Adverse Events

6.1.1.4.1. Main Analysis

- Estimand: The percentage of participants reporting SAEs from the study vaccination through 6 months after the study vaccination (Section 2.2).
- Analysis set: Safety population (Section 4).
- Analysis time point: From the study vaccination through 6 months after the study vaccination.
- Analysis methodology: Descriptive statistics (Section 5.2.1).
- Intercurrent events and missing data: Missing data will not be imputed except for partial AE start dates (Section 5.3).
- Reporting results: Counts, percentages, and the associated Clopper-Pearson 95% CIs of SAEs from the study vaccination through 6 months after the study vaccination will be provided for each group.

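### The sponsor may stop study visits after reviewing a group's data, and nothing reconciles this with the primary 6-month SAE endpoint

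*Protocol*

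**What the plan says.** **The discretion.** In Protocol Section 4.1 the trigger and the decision-maker are given as "Based on review of safety or immunogenicity data of any study intervention group, at Pfizer's discretion". Later blood sampling in that "group may be halted and/or not analyzed and study visits or other procedures may be discontinued". The introduction to the Schedule of Activities (Section 1.3) says that "study visits, blood sample collection/analysis, or other procedures may be halted or discontinued". SAP Section 2.3 has the same provision: sampling "may be halted and/or not analyzed, and study visits or other procedures may be discontinued". No criterion is stated. Section 4.1 mentions the external data monitoring committee but does not make a stop depend on its recommendation.

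**Who decides, and on what.** Section 6.4.3 states that in Cohorts 1, 2 and 4 "the majority of Pfizer/BioNTech staff will be unblinded to study intervention allocation". Section 9.4 adds that "Pfizer may conduct unblinded reviews of the data during the course of the study". Section 9.4.1 plans an analysis of each cohort's data through Visit 3.

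**The endpoint.** The SAE estimand in SAP Section 6.1.1.4.1 is "The percentage of participants reporting SAEs from the study vaccination through 6 months after the study vaccination". It is analysed on the safety population. Only partial AE start dates are imputed, and nothing adjusts for length of follow-up.

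**Collection.** Protocol Section 8.4.1 has SAEs collected from consent through Visit 5, about 6 months. In Sections 8.10.4 and 8.10.5 (Visits 4 and 5), the immunogenicity blood draw may be waived by the sponsor, while AE recording carries no such condition. Section 7.2.1 keeps safety follow-up going when a participant asks to stop active participation. No section says the same for a stop that the sponsor initiates.

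**The concern.** Each participant receives one dose at Visit 1. A later halt to visits therefore removes no exposure, only observation. The trigger includes immunogenicity results, so a group could lose visits because its 1-month titers disappointed, while the other groups in the same cohort continue to Visit 5.

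The primary 6-month SAE percentages would then be set side by side with equal status but unequal follow-up, and the shorter follow-up would fall in a group chosen by its results. The SAP has no rule for this case: a participant last seen at Visit 3 without an SAE counts the same as one followed to Visit 5 without an SAE. The point matters most in Cohort 4, where Section 4.2 describes several of the candidates as not previously studied clinically. From Cohort 4 onwards, the myocarditis and pericarditis window in Section 8.4.8 is 6 weeks (42 days), which ends after the Visit 3 window closes at day 35.

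**Working it through.** **Inputs.** Group sizes: 60 in Cohort 4 (Table 4), 100 in each Cohort 2 group (Table 1). Visit windows from Section 1.3: Visit 3 at day 28-35, Visit 4 at day 84-98, Visit 5 at day 175-189 (midpoint 182). The documents give no 6-month SAE rate and no hazard shape. The rates below are assumptions taken from the Table 8 grid, and a constant hazard is assumed.

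**Step 1: reproduce the plan's figure.** P(at least 1 event) = 1 - (1 - p)^N. For p = 2%, N = 60: 1 - 0.98^60 = 0.702, against 0.70 in Table 8. For N = 100: 0.867, against 0.87. All 36 cells of Table 8 reproduce.

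**Step 2: rate observed if follow-up ends on day d.** q = 1 - (1 - p)^(d/182). With p = 2%:

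- Stop after Visit 3: q = 0.31% (d = 28) to 0.39% (d = 35).
- Stop after Visit 4: q = 0.93% (d = 84) to 1.08% (d = 98).

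The expected reported percentage is therefore about 15-19% of the true 2% after a Visit 3 stop, and about 46-54% after a Visit 4 stop.

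**Step 3: chance of seeing at least one SAE, 1 - (1 - q)^N.**

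| N | Assumed 6-month rate | Full follow-up | Stop after Visit 3 | Stop after Visit 4 |
|---|---|---|---|---|
| 60 | 1% | 0.45 | 0.09-0.11 | 0.24-0.28 |
| 60 | 2% | 0.70 | 0.17-0.21 | 0.43-0.48 |
| 60 | 5% | 0.95 | 0.38-0.45 | 0.76-0.81 |
| 100 | 2% | 0.87 | 0.27-0.32 | 0.61-0.66 |

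**Step 4: sensitivity.** Replacing 182 days by 175 or 189 for N = 60 and 2% gives 0.16-0.22 after Visit 3 and 0.42-0.49 after Visit 4. If SAE collection to 6 months continues when blood draws or clinic visits stop, the figure stays at 0.70.

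**Step 5: the provisions side by side.** Sections 1.3 and 4.1 and SAP Section 2.3 let visits be discontinued. Section 8.4.1 defines SAE collection by reference to Visit 5, one of the visits that may be discontinued. Sections 8.10.4 and 8.10.5 treat only the blood draw as optional. No provision says which prevails.

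**The case against.** The strongest reply is that the clause is permissive while the SAE duty is not. SAEs are to be collected through Visit 5 (Section 8.4.1), reported through about 6 months (Section 8.4.1.1), and the SAP repeats the period (Section 3.1.1.5). None of these contains a sponsor opt-out. The visit procedures point to a narrower intended use, in which only blood draws are dropped. This stands, and it rules out a reading that a reader might reach for: that the clause cancels the primary endpoint in a stopped group. The documents support an unreconciled conflict, not a decision to end SAE collection.

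Other ascertainment may also continue. Participants are asked at Visits 1 to 4 to report medically attended events and hospitalizations (Section 1.3), and they receive weekly illness-diary reminders (Section 8.3.4). So a reader who infers that a Visit 3 stop loses five-sixths of SAE follow-up is assuming that every such route closes, which is not stated. Unprompted reports are still not equivalent to scheduled questioning. An even hazard may also overstate the loss of vaccine-related events: Section 2.3.1 says myocarditis and pericarditis cases typically occur within 14 days.

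Group-only stopping is partly inference. In Section 4.1 the restriction to the reviewed group is attached to blood sampling and is not repeated for visits. The trigger is group-specific, though, so it is the natural reading.

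Finally, a stop would be partly visible, because SAP Section 6.5.2.1 tabulates completion and withdrawal with reasons by group. That does not correct the SAE percentage itself.

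**Conclusion.** The point holds as an unreconciled provision with a real consequence if used. The plan gives a largely unblinded sponsor discretion to discontinue visits on a group's results, exempts no safety follow-up, and has no analysis rule for a group so stopped. Used as written, without another means of soliciting SAEs, it would understate that group's primary SAE percentage relative to the others.

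For a group of 60 and a 2% rate, the chance of seeing at least one SAE would fall from 0.70 to 0.17-0.21 (stop after Visit 3) or 0.43-0.48 (stop after Visit 4). This rests on a constant hazard, an assumed rate and no ascertainment after the stop, so it is an upper bound on the loss under that hazard, not a forecast.

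Two wider inferences are not supported. The formal tests in Cohorts 2 and 3 combined use 1-month titers and would be affected only by a stop before Visit 3. The month-3 and month-6 titers are exploratory and summarised within group, so one group's absence does not bias another group's estimate.

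**What to change.** In Protocol Sections 1.3 and 4.1 and SAP Section 2.3, state that:

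- a stop based on immunogenicity data applies to immunogenicity sampling and assays only;
- AE collection through Visit 3 and SAE collection through 6 months continue for every vaccinated participant, by telephone where no blood is drawn.

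This leaves the discretion to act on safety data unchanged, and brings the three passages into line with Sections 8.4.1, 8.10.4 and 8.10.5.

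In the SAP, add that any stop and the follow-up time will be reported by group, with an exposure-adjusted SAE rate if follow-up differs between groups.

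The cost is a few sentences in three places plus one SAP rule. The contacts are already in the schedule. The small downside is continued safety contact with participants in a group that is no longer being developed. The sponsor can still drop a candidate and save its blood draws and assays.
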